11.8 Efficacy Analyses

All efficacy parameters will be summarized over the ITT analysis set overall and by DB treatment group. Summaries of efficacy endpoints by visit will be performed using OC and LOCF methods.

Time to event parameters, such as the time from treatment success to subsequent worsening (PGA ≥ 2) or duration of treatment episode, will be summarized by the Kaplan-Meier product limit method using OC. Median time to event will be estimated. If the median time is not determined, other percentiles will be estimated.

The remaining efficacy endpoints will be summarized descriptively as follows: continuous data will include the mean, SD, minimum, maximum, median, and number of observations; descriptive summary statistics for categorical data will include frequency counts and percentages.

For the following efficacy outcomes:

1. Proportions of subjects who achieve PGA = 0 at least 1 time during the study (for subjects entering the study with a PGA score ≥ 1):
2. Proportions of subjects who experienced PGA ≥ 2 at least 1 time during the study (for subjects entering the study with a PGA score = 0):
3. PGA scores at Week 40 (LOCF)
4. BSA [REDACTED] change from baseline to Week 40 (LOCF)
5. PASI [REDACTED] change from baseline to Week 40 (LOCF)

subgroup analyses will be generated for the following groupings:

- Baseline PGA
- Age (<65 and ≥ 65 years old)
- Sex
- Race (White, Other)
- Baseline % BSA affected – ($<10\%$, $\geq 10\%$)
- Duration of disease (<5 years, 5-10 years, >10 years)
- Country (USA and Canada)

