A subject is considered to have completed the study when he/she completes all required procedures/visits for the 40-week (Visit 11) treatment period. The end of the study is defined as when the last active subject has completed the Follow-up Visit.

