6. SAMPLE SIZE DETERMINATION

The sample size of this study is based on the ICH E1 guideline on extent of population exposure to assess clinical safety for drugs intended for long-term treatment of non-life-threatening conditions. An estimated 850 subjects who complete Study DMVT-505-3001 or Study DMVT-505-3002 will be enrolled in this study at approximately 100 to 120 study sites in the US and Canada. A high discontinuation rate is anticipated in this long-term extension study. Approximately 300 subjects are expected to complete the study (40 weeks of treatment).

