8. HANDLING OF MISSING DATA

Efficacy endpoints will be summarized by visit using observed cases (OC) and last observation carried forward (LOCF) methods as appropriate. Baseline values will not be carried forward.

Imputation of Start and End Dates of Adverse Event (AE)

To calculate duration of Adverse Events, the following rules will be used where applicable to impute partial or completely missing start dates or end dates:

- If only the day is missing for a start date, the 1st of the month will be imputed. If the new estimated date falls before the Visit 1 date, while the known month and year match the month and year of the Visit 1 date, the date of Visit 1 will be used as the new estimated date.
- If only the day is missing for an end date, the last day of the month will be imputed. If the new estimated date falls after the date of last study visit, the date of last study visit will be used as the new estimated date.
- If both the day and the month are missing for a start date or end date, no imputation will be used, and the duration will not be calculated.
- If the start date or end date is completely missing, duration will not be calculated.

For AEs ongoing at the end of pivotal studies, duration will be computed using the DMVT-505-3003 visit 1 date as the AE start date.

If relationship of AE to treatment is missing, the event will be conservatively considered as being related to study drug. Missing AE severity will be imputed to the highest severity level (most severe). Through the data cleaning process, all attempts will be made to avoid missing values for relationship and severity.

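### The Week-40 subgroup results for PGA, BSA and PASI are planned by LOCF alone, although on the plan's own figures most of those values would be carried forward from earlier visits

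*SAP*

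**What the plan says.** **Subgroup analyses.** SAP 11.8 names five outcomes to be broken down by baseline PGA, age, sex, race, baseline %BSA, disease duration and country. Outcomes 1 and 2 are proportions reaching a PGA state at least once. Outcome 3 is "PGA scores at Week 40 (LOCF"). Outcomes 4 and 5, for BSA and PASI, are each a "change from baseline to Week 40 (LOCF"). None of these three has an observed-case version.

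**Main summaries.** The same section says "Summaries of efficacy endpoints by visit will be performed using OC and LOCF methods", overall and by double-blind treatment group. SAP 11.7 labels the by-visit BSA and PASI endpoints with both methods.

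**Expected retention.** SAP 6 says "An estimated 850 subjects who complete Study DMVT-505-3001 or Study DMVT-505-3002 will be enrolled in this study", that "A high discontinuation rate is anticipated in this long-term extension study", and that "Approximately 300 subjects are expected to complete the study (40 weeks of treatment"). SAP 3 defines completion: "A subject is considered to have completed the study when he/she completes all required procedures/visits for the 40-week (Visit 11) treatment period".

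**Rules that affect LOCF.** SAP 8 says "Baseline values will not be carried forward". SAP 10.5 re-numbers an early-termination visit to the next nominal visit, so it counts as Week 40 only when Visit 10 was the last one attended.

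**Treatment scheme.** SAP 3 has drug stopped at PGA 0 and restarted at PGA 2 or more, in a pattern that runs until Week 40.

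**The concern.** LOCF at Week 40 is a fair summary when few values are carried, or when the outcome has levelled off before people leave. Neither can be assumed here. The plan itself expects most subjects to leave before Week 40, and the stop/restart scheme means disease status is expected to move. A subject who leaves while clear carries PGA 0 to Week 40. A subject who leaves during a worsening carries PGA 2 or more. Either value may be many weeks old.

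Subgroup tables are where this matters most, because they invite comparison. If older and younger subjects, or US and Canadian subjects, tend to withdraw at different times, their LOCF values come from different weeks. A difference labelled Week 40 could then come from withdrawal timing. With no OC result, no n observed and no indication of how old the carried values are, the reader cannot tell.

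**Working it through.** **Inputs.** Enrolment 850 and completers about 300 (SAP 6). Completion means finishing Visit 11 (SAP 3). Ten 4-week intervals run from Visit 1 to Week 40 (SAP 3). Baseline is not carried forward (SAP 8). Early-termination visits are re-numbered (SAP 10.5). The plan states no dropout rate and bases its sample size on ICH E1 exposure, so there is no plan figure to reproduce beyond the division in step 1.

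**Step 1: ceiling from dropout alone.** (850 − 300)/850 = 550/850 = 64.7%.

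**Step 2: allow for the two SAP rules.** Let *b* be the subjects with no post-baseline value, who leave the LOCF denominator. Let *e* be the withdrawals whose early-termination visit becomes Week 40. The carried-forward share is

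(550 − *b* − *e*) / (850 − *b*).

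**Step 3: assume constant dropout per interval (not stated in the plan).** Retention per interval is (300/850)^(1/10) = 0.901. About 850 × (1 − 0.901) ≈ 84 leave in the first interval. About 850 × 0.901^9 − 300 ≈ 333 − 300 = 33 leave in the last.

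| Early-termination visits | *b* | *e* | Carried-forward share |
|---|---|---|---|
| All attended | 0 | 33 | 517/850 = 60.8% |
| None attended | 84 | 0 | 466/766 = 60.8% |
| Missed in first interval, attended in last | 84 | 33 | 433/766 = 56.5% |
| Attended in first interval, missed in last | 0 | 0 | 550/850 = 64.7% |

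If attendance is the same in every interval, the share is 60.8% whatever that attendance is. The third row is the most favourable case. The fourth is the ceiling again.

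**Step 4: what would bring the share below half.** Any one of these, taken alone:

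- more than 250 subjects with no post-baseline value, since (550 − 250)/(850 − 250) = 300/600 = 50%;
- more than 125 early-termination visits landing on Week 40, since (550 − 125)/850 = 425/850 = 50%;
- more than 425 completers, since 425/850 = 50%.

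**Step 5: can withdrawal timing alone separate subgroups?** This is an illustration, and its response and retention figures are assumptions. Two subgroups have the same response, rising linearly from 20% at Week 4 to 60% at Week 40. Dropout is constant per interval and unrelated to response. The last scheduled visit is carried forward, and subjects with no post-baseline value are excluded. LOCF response is then 20% + 40% × (mean week of last visit − 4)/36.

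- Subgroup retaining 20%: mean last visit about Week 21.5, LOCF 39.5%.
- Subgroup retaining 60%: mean last visit about Week 32.1, LOCF 51.3%.

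The gap is about 12 points, although both truly stand at 60%. If response instead falls from 60% to 20%, the figures are 40.5% and 28.7%, a 12-point gap the other way. If response is flat, the gap is zero. At the planned 35.3% retention (300/850) with the rising course, LOCF gives 44.6%, and the median carried value is 24 weeks old.

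**The case against.** Four points on the other side carry weight.

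**OC at Week 40 is not absent from the analysis.** SAP 8 and 11.8, and Protocol 10.4.2 and 10.6, plan both methods for by-visit summaries. SAP 11.1 also plans Kaplan-Meier curves of days in study. A reader might infer that the trial's Week-40 results rest on LOCF alone; they do not. This stands, and it limits the point to the subgroup tables. The main tables are split by double-blind treatment group only, so they do not help a reader who compares age, severity or country groups.

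**The on-drug/off-drug mix is not an LOCF fault.** A reader might blame LOCF for mixing subjects in remission off drug with subjects under treatment. That mix comes from the design and is equally present in values observed at Week 40. Adding OC would not remove it.

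**OC is not the true answer.** Completers are expected to be about 35% of subjects and are a selected group. The gap between LOCF and OC does not measure bias.

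**The study is descriptive.** SAP 10.1 rules out statistical testing, so no error rate or formal conclusion is at risk. This keeps the severity low.

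It might also be said that the planned table shells already include OC. The outline in SAP section 15 is not visible in the public text, so this cannot be checked. The wording of SAP 11.8 specifies LOCF alone.

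**Conclusion.** The point holds for subgroup outcomes 3 to 5. As written, the SAP gives each subgroup a Week-40 figure made up mostly of earlier observations and gives no means of seeing this. The carried-forward share is about 57-61% under constant dropout, with 64.7% as the ceiling from dropout alone. Both rest on planning figures of 850 and about 300, which the plan calls an estimate and an approximation. The share in any one subgroup is unknown, because dropout by subgroup is not given.

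A reader might infer that subgroups with different withdrawal timing are bound to differ. The documents support only that they may. A spurious difference needs response to change over time, or withdrawal to depend on disease state. Its direction cannot be known in advance, as step 5 shows.

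Nor do the documents support a demand for multiple imputation or a repeated-measures model here. More than half of the Week-40 values would be model-driven, and treatment state after withdrawal is not observed. That is a trade-off, not a correction.

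The consequence is limited to how descriptive subgroup summaries are interpreted. Severity is minor.

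**What to change.** In SAP 11.8, change the label on outcomes 3, 4 and 5 from LOCF to OC and LOCF, matching the by-visit endpoints in SAP 11.7. For each subgroup level, show next to the LOCF result:

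- the OC result and its n;
- the number of carried-forward values;
- their median age in weeks (40 minus the nominal week of the value carried).

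Add a footnote that OC describes completers, plus any early-termination visits re-numbered to Week 40, and that these are a selected minority.

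The change uses data and methods already in the SAP and needs no new collection. The cost is a few more columns or tables, and Week-40 subgroup figures that look less tidy. If only one element can be added, it should be the OC result with its n.

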11.9 Health-related Quality of Life

The DLQI was assessed at 4-week intervals to measure the impact of tapinarof cream, 1% on quality of life in adults with plaque psoriasis.:

The DLQI is a 10-item PRO measure that assesses the extent to which the skin condition has affected the subject's quality of life over the past week, including 6 domains (daily activities, personal relationships, symptoms and feelings, leisure, work/school, and treatment). The total score (0-30) is the sum of 10 questions with each ranging from 0 to 3. The scoring of each question (for Question 7 see below) is as follows:

Response	Score
Very much	3
A lot	2
A little	1
Not at all	0
Not relevant	0
Question unanswered	0

Question 7: Over the last week, has your skin prevented you from working or studying?	Question 7A: If “No”, over the last week how much has your skin been a problem at work or studying?	Score
Yes	Any response	3
No	A lot	2
No	A little	1
No	Not at all	0
Not relevant	Any response	0

If one question is left unanswered this is scored 0 and the scores are summed and expressed as usual out of a maximum of 30. If two or more questions are left unanswered the total DLQI score is missing.

When summarizing the domain scores, if a domain contains two questions and the answer to one of the questions is missing, that domain will be scored as the answer to the non-missing question. If all the answers to questions in a domain are missing, the domain will not be scored.

DLQI total score and subscores on DLQI domains and their changes from baseline as well as percent change from baseline values will be summarized descriptively. The following table identifies the DLQI domains and the questions that are summed in order to calculate them.

Domain	Questions
Symptoms and feelings	1 and 2
Daily activities	3 and 4
Leisure	5 and 6
Work and school	7
Personal relationships	8 and 9
Treatment	10

11.10 Patient Satisfaction Questionnaire

[REDACTED]

11.11 Safety Analysis

All safety parameters will be summarized over the ITT population of all enrolled subjects, overall and by DB treatment group.

11.11.1 Adverse Events

AE terms will be coded using Medical Dictionary for Regulatory Activities (MedDRA) dictionary. All AEs reported in current study are considered as treatment-emergent AE (TEAE) except for those AEs ongoing at the end of pivotal studies but resolved prior to the Visit 1 date in the extension study.

All TEAEs will be listed by subject, detailing the verbatim term given by the investigator, the preferred term (PT), system organ class (SOC), onset date and time, end date and time, ongoing at the end of pivotal studies (Y/N), duration (days), CTCAE grade, outcome, relationship to study drug, action taken with study drug, other action taken to treat the event, AE of special interest (Y/N), seriousness and criteria for seriousness.

AEs resolved prior to the Visit 1 date, Serious TEAEs (STEAEs), TEAEs leading to study discontinuation and TEAEs related to study drug will also be listed separately. The following adverse events of special interest (AESIs) will be identified and listed separately: contact dermatitis, folliculitis, and headache.

The number and percent of subjects with TEAEs will be summarized as incidence rates of:

- Any TEAE
- Any TEAE Excluding Those Ongoing at the end of the Pivotal Studies
- Any TEAE Ongoing at the end of the Pivotal Studies
- Any treatment-emergent AESIs
- Any treatment-emergent AESIs Excluding Those Ongoing at the end of the Pivotal Studies
- Any treatment-emergent AESIs Ongoing at the end of the Pivotal Studies
- Any treatment-related TEAE
- Any TEAE leading to study drug discontinuation
- Any TEAE leading to study discontinuation
- Any serious TEAE

- Death
- Treatment-related Serious TEAE
- Serious TEAE leading to study drug discontinuation
- Serious TEAE leading to study discontinuation
- TEAE (COVID-19)

Individual PTs will be summarized by SOC in alphabetical order and PT in descending order of frequency for the following subsets and subgroupings:

- All TEAEs
- All TEAEs by maximum CTCAE grade
- All TEAEs by maximum causality (not related, related) to the study drug
- All TEAEs Excluding Those Ongoing at the End of the Pivotal Studies
- All TEAEs ongoing at the end of the pivotal studies
- All treatment-related TEAEs
- All TEAEs leading to study discontinuation
- All TEAEs leading to study drug discontinuation
- All serious TEAEs

All TEAEs and all serious TEAEs will also be summarized by SOC (alphabetical order) and PT (descending order) for the following subgroups:

- Age (<65 and \geq 65 years old)
- Sex
- Race (White, Other)

Furthermore, TEAEs will be categorized by day of onset among the following 4 categories:

- \leq 12 weeks
- >12 to \leq 24 weeks
- >24 to \leq 40 weeks
- >40 weeks.

For each of these categories, TEAEs will be summarized by SOC in alphabetical order and PT in descending order of frequency. TEAEs ongoing at the end of the pivotal studies will be considered in the first category (i.e. day of onset \leq 12 weeks).

At each level of summarization, a subject will be counted once if he/she reported one or more events. The severity of TEAEs and relationship to study drug will be summarized in a similar

manner. For summaries of relationship to study drug, a subject will be classified according to the closest relationship. For summaries of TEAE CTCAE grade, a subject will be classified according to the worst grade.

For AESIs, summarization will be more extensive, reflecting the more detailed information collected. Information summarized will include number of events per subject, earliest onset day, duration (in days), causality, grade and seriousness of AESIs, outcome, actions taken, assorted physical characteristics of the AESIs, and demographic/baseline characteristics and PGA status of the subjects experiencing them. Each type of AESI will be summarized separately. If a subject has more than one treatment-emergent occurrence of an AESI, the subject's maximum duration, highest levels of causality and seriousness, maximum grade and generally the most extreme level of each characteristic will be summarized. If an AESI was ongoing at end of study (EOS), it will not be included in the duration summary. AESIs ongoing at the end of pivotal studies will also be included in the summary.

A Kaplan-Meier figure will be generated for each AESI of time to first event for events starting during the study. Subjects not experiencing the AESI will be censored at the date of study completion or discontinuation. AESIs ongoing at the end of pivotal studies will not be included.

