6.3. Safety Assessments

6.3.1. Adverse Events

All AEs will be collected from the time the subject signs the ICF until the final visit/contact with the subject. Adverse events that began during the pivotal study and were ongoing at the end of that study will be reported as ongoing AEs. Additional safety information, including the definition of an AE and the methods for recording, evaluating, and assessing causality of AEs and the procedures for completing and transmitting SAE reports are provided in Section 8.

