10.4.3. Safety Analyses

The number and percent of subjects with TEAEs will be summarized by system organ class and preferred term for all TEAEs, all TEAEs considered by the Investigator to be related to study drug, all SAEs, and all TEAEs leading to study drug discontinuation. All adverse event summaries will include information for adverse events that occurred after administration of the first dose of study drug until completion of the final study visit. Data listings will be provided for subjects who discontinued the study due to an adverse event and for subjects with an SAE.

Selected clinical laboratory data will be analyzed using descriptive summary statistics, including the number of nonmissing observations, mean and SD, median, upper and lower quartiles, minimum and maximum for values and changes from Baseline. Categorical safety data will be analyzed using frequency tables and, if applicable, shift tables.

Vital signs will be listed by subject and summarized by visit.

Mean scores from the LTS will be summarized by visit.

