7. ANALYSIS POPULATIONS

Intent-To-Treat (ITT) Analysis Set: includes all subjects enrolled into the study. All subjects who signed the informed consent will have enrolled in the study. All efficacy and safety analysis will be performed over ITT analysis set.

Subjects will be analyzed overall and by the original treatment assigned in pivotal studies (DMVT-505-3001 and DMVT-505-3002). This will be referred to below as DB (double-blind) treatment group.

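### The SAP's TEAE definition admits carried-over events and events in undosed subjects, an undeclared departure from the protocol, and the grade, causality, serious, discontinuation, subgroup and onset-period tables have no version without carry-over

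*SAP*

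**What the plan says.** Protocol 10.4.3 sets the window for safety reporting: "All adverse event summaries will include information for adverse events that occurred after administration of the first dose of study drug", up to the final visit. Protocol 6.3.1 brings older events into the extension database: "Adverse events that began during the pivotal study and were ongoing at the end of that study will be reported as ongoing AEs".

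SAP 11.11.1 replaces the protocol's window with a different rule: "All AEs reported in current study are considered as treatment-emergent AE (TEAE) except for those AEs ongoing at the end of pivotal studies", with the exception confined to those that had ended, "but resolved prior to the Visit 1 date in the extension study". The rule mentions neither dosing nor worsening. The population adds no dosing condition either: "All safety parameters will be summarized over the ITT population of all enrolled subjects" (SAP 11.11), and "All subjects who signed the informed consent will have enrolled in the study" (SAP 7).

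Two further conventions follow. For events open at the end of the pivotal study, "duration will be computed using the DMVT-505-3003 visit 1 date as the AE start date" (SAP 8). In the tables by time of onset, SAP 11.11.1 assigns these same events to the category of 12 weeks or less.

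SAP 12 lists changes to the LTS summary and the satisfaction questionnaire, and the COVID-19 additions. It does not list the TEAE rule, although the SAP revision history records that the definition was updated in Amendment 2.

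**The concern.** Safety and tolerability is the first objective of the study, and a data-cut is planned for the marketing application. A reader of a TEAE table expects events that arose, or got worse, after study drug was started. Under the SAP rule two other kinds of event enter by design.

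- **Carried-over events.** Subjects come from the tapinarof or the vehicle arm of a pivotal study (Protocol 3.1). An event that began under vehicle and is unchanged at Visit 1 counts as treatment-emergent here.
- **Events without extension exposure.** A subject who enters with PGA 0 gets no drug unless PGA reaches 2 or more. If that never happens, every event the subject reports is still a TEAE. If the subject came from vehicle, there has been no tapinarof in either study.

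The effect is not simply conservative. Loading old events into the first onset period can make event occurrence seem to fall with time, which is the very pattern those tables are read for. Timing AESIs from Visit 1 makes carried-over contact dermatitis, folliculitis and headache look shorter than they were.

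**Working it through.** The plan gives no figure to reproduce. The study is descriptive, and its sample size rests on ICH E1 rather than on a calculation. The check compares the texts and then illustrates the size.

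**1. How much the exception removes.** It drops carried-over events that ended before Visit 1. SAP 10.3 says that Visit 1 is also the last pivotal visit. Where the two dates coincide, an event open at the end of the pivotal study cannot have ended before Visit 1, so nearly all carried-over events stay in.

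**2. Which tables have a version without carry-over** (counted from SAP 11.11.1).

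| Output | Split | Not split |
|---|---|---|
| 15 incidence lines | 6: any TEAE and any AESI, each in total, without and only carry-over | 9: related, serious, discontinuation, death, COVID-19 and combinations |
| 9 SOC/PT summaries | 3: all TEAEs in total, without and only carry-over | 6: maximum grade, maximum causality, related, two discontinuation tables, serious |
| Age, sex and race subgroups | none | all |
| 4 onset periods | none | all |
| AESI Kaplan-Meier figure | carry-over omitted | – |
| AESI detail summary | – | carry-over included |

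The last two rows mean that AESI counts in the figure and in the summary need not agree. No output is limited to dosed subjects or to events after the first extension dose.

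**3. Size of the carry-over effect.** Let p be the share of subjects with a new-onset event and c the share with a carried-over event, taken as independent. Unsplit incidence is 1 − (1 − p)(1 − c), so the excess over p is c(1 − p). The documents give neither input; c = 5-20% and p = 20% or 50% are assumptions.

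- p = 50%: 0.05 × 0.50 = 2.5 points; 0.20 × 0.50 = 10 points.
- p = 20%: 0.05 × 0.80 = 4 points; 0.20 × 0.80 = 16 points.

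For a given table, c is the share with a carried-over event of the type tabulated, so it will be smaller for serious events than for all events.

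**4. Size of the undosed effect.** Let u be the share never dosed in the extension, assumed to be 2-10%, with the same p as in dosed subjects. With the planned 850 enrolled, 850 × u × p subjects are counted who would not be under a first-extension-dose rule: 3.4 to 17 at p = 20%, and 8.5 to 42.5 at p = 50%.

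**5. Both together**, at c = 10%, u = 5%, N = 850:

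| | p = 20% | p = 50% |
|---|---|---|
| SAP any TEAE | 238 (28.0%) | 468 (55.0%) |
| SAP without carry-over | 170 (20.0%) | 425 (50.0%) |
| After first extension dose | 162 (19.0% of 850; 20.0% of dosed) | 404 (47.5% of 850; 50.0% of dosed) |

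**6. Onset periods.** The excess c(1 − p) falls wholly in the first period. Suppose new-onset incidence is 20% in each of the first two periods, both 12 weeks long, and ignore dropout. The tables would then show 24-36% followed by 20%: a decline produced by the rule alone.

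**7. AESI duration.** An event that began d days before Visit 1 and ended e days after it lasted about d + e days; the SAP reports about e. For an event that began during the 12-week pivotal treatment period, d can reach about 84 days (12 × 7).

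**The case against.** A reader might infer that the TEAE tables as a whole fail to measure events in the extension. The documents do not support that. The headline any-TEAE, any-AESI and all-TEAE SOC/PT results each have a version without carried-over events, the listing flags those events, and the AESI Kaplan-Meier figure omits them. A reader might also infer that vehicle-onset events are hidden. They are not: safety results are also shown by pivotal treatment group, so only the overall column mixes them.

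Other points limit the reach of the concern.

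- Protocol 4.3 excludes subjects with a potentially treatment-related SAE, or an event leading to permanent discontinuation, in the pivotal study. Little carry-over should reach the related-serious line. A carried-over event in a discontinuation table must have led to stopping in this study, which is worth knowing.
- Protocol 10.4.3 does not tie the first dose to the extension. For former tapinarof subjects it could mean the pivotal dose, and the conflict would then shrink to former vehicle subjects: their carried-over events, and any events before they first receive tapinarof. Protocol 5.1.1 describes study drug as tapinarof cream for up to 40 weeks, which favours the extension reading without settling it.
- Subjects entering with PGA 1 or more are due to apply drug at Visit 1, so nearly all their new events are post-dose under either rule.
- The protocol's own window covers "adverse events that occurred after administration of the first dose of study drug until completion of the final study visit", which includes drug-free intervals. It does not isolate events on drug, so rates on and off drug per person-time would be a refinement and not a protocol requirement.

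All of this narrows the point. None of it supplies the missing splits, a dosed-only table, or a declaration in SAP 12.

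**Conclusion.** The point holds in limited form. The SAP's TEAE rule differs from Protocol 10.4.3 and is not declared as a change. The practical fault lies in the tables without a split: maximum grade, causality, treatment-related, serious, discontinuation, age/sex/race and onset period. AESI durations are also affected. The onset-period tables are the clearest case, because the bias has a known direction and falls entirely on the first period.

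The size cannot be fixed from the documents, which report neither how many subjects carry over an event nor how many are never dosed. The ranges in steps 3 to 5 are conditional on the assumed rates, on independence of carried-over and new events, and on equal incidence in dosed and undosed subjects. The any-TEAE excess is the least troublesome, since a clean companion line is already planned. This should be corrected, but it does not undermine the headline safety summaries.

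**What to change.** 1. Define a TEAE as an adverse event with onset, or recorded worsening, on or after the first application of study drug in the extension. The documents do not describe how grade changes over time are captured, so the worsening part applies where such a change is recorded.
2. Use that definition in the maximum-grade, causality, related, serious, discontinuation, subgroup and onset-period tables.
3. Tabulate separately the carried-over events, and the events before first dose or in never-dosed subjects. Carried-over events that lead to discontinuation then stay visible.
4. Compute adverse event duration, including AESI duration, from the true onset date.
5. List any remaining departure from Protocol 10.4.3 in SAP 12.

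The cost is a few extra tables and some reprogramming. The carry-over flag and onset date are already in the planned listing, and first-dose dates can be taken from the dose diary and the in-clinic dosing records.
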